11.4 Exploratory Objectives

- Determine geometric agreement between breath-hold positions as determined by a novel surface guidance system vs. concomitant breath-hold CBCT image sets. Geometric agreement will be evaluated by average symmetric surface distance (ASSD), modified Hausdorff distance (MHD), and Dice similarity coefficient measurements.
- Evaluate the compatibility of a standard-of-care respiratory gating system and the novel surface-guidance system for concomitant use. This will be evaluated qualitatively.
- Determine the minimum safe planning target volume (PTV) and planning organ-at-risk volumes (PRV) to be subsequently utilized with the novel surface guidance system. This will be determined through measurement evaluations in the first exploratory endpoint.
- Determine the local, in-field control rate at three months post-treatment. This will be determined by the treating physicians using RECIST criteria.
- Determine acute toxicity rates at three months post-treatment. This will be assessed by a qualitative description of grade 3 or higher non-hematologic toxicity events related to radiation therapy at three months post-treatment.
- Identify patient and or treatment factors that maximize the potential efficacy of surface guided breath-hold respiratory gating. These include factors such as surface topography features as well as skin tone. This will be evaluated qualitatively.

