	
 2. Evaluate the compatibility of a standard-of-care respiratory gating system and the novel surface-guidance system for concomitant use. 3. Determine the minimum safe planning target volume and planning organ-at-risk volumes to be subsequently utilized with the novel surface guidance system. 4. Determine the local, in-field control rate at three months post-treatment. 5. Determine acute toxicity rates at three months post-treatment. 6. Identify patient and or treatment factors that maximize the potential efficacy of surface guided breath-hold respiratory gating.
Endpoints:	
Primary Endpoint: Percentage of scheduled treatment fractions delivered successfully using the surface guidance system. Success will be defined as delivery of a given treatment fraction in one on-table attempt, without requiring use of a secondary (backup) motion management system, or alternative treatment machine. Unsuccessful delivery of a fraction will be defined as multiple attempts for gating without reproducible positioning, breath-hold, and/or surface guidance feedback, such that the fraction is abandoned.
 
Exploratory Endpoints:
 
 1. Geometric agreement between breath-hold positioning as determined by a novel surface guidance system compared with standard of care concomitant breath-hold CBCT image sets, as evaluated by average symmetric surface distance (ASSD), modified Hausdorff distance (MHD), and Dice similarity coefficient measurements. 2. Qualitative evaluation of the compatibility of a standard-of-care respiratory gating system and the novel surface-guidance system for concomitant use. 3. Quantitative and qualitative measurement of minimum planning target volume (PTV) margins and planning organ-at-risk volumes to be subsequently utilized with the novel surface guidance system as determined through measurement evaluations in exploratory endpoint 1. 4. Local, in-field control rate at three months post-treatment will be determined as part of standard-of-care clinical evaluation by the treating physicians, using RECIST criteria. 5. Qualitative description of acute (within 90 days) Grade 3 or higher non-hematologic toxicity events related to radiation therapy at three months post-treatment. 6. Qualitative description of patient and treatment site factors, such as unique patient surface topography or skin tone, that

	might impact surface imaging tracking at the region of interest.

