11.2 Sample Size

The primary endpoint of this study is to assess the feasibility of surface-guided, respiratory gated delivery of CT-guided stereotactic radiotherapy for upper abdomen and lower thorax malignancies by confirming that gated treatment can be delivered successfully in more than 75% of scheduled treatment fractions using a novel surface guidance system. A total of 10 evaluable patients (as defined in Section 5.2) will be included, with five treatment fractions each, for a total of $n = 50$ evaluable fractions. In order to assess the feasibility of the gating methodology on the novel surface guidance system, we conducted a one-sample reliability demonstration test based on the binomial distribution. The study will be powered based on an expected success rate of 95% and a minimum accepted rate of 75%. With 10 patients and 5 fractions per patient, 50 total fractions ($n=50$) would be assessed. In-patient correlation is anticipated, as surface-guided delivery is in part patient-surface dependent, with an anticipated value of 0.2. With a one-sided alpha of 0.25 and $n=50$ fractions across 10 unique patients, we would have a minimum of 92% power to detect feasibility of successful gated delivery.

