11.5 Statistical Analysis Plan

Our principal objective in this trial will be to determine the feasibility of surface guided, respiratory gated delivery of CT-guided stereotactic adaptive radiotherapy (CT-STAR) in the abdomen and lower thorax using a novel surface-guidance system. Given that no prior data exists for thoracic or abdominal SBRT using this surface guidance system for respiratory gating, we will also report descriptive statistics for treatment adaptation, dosimetry, geometric and phase agreement between the novel surface guidance system and CBCT, acute toxicity, in-field control rates, and minimum acceptable PTV and PRV expansions for treatment planning. As a pilot study we will establish these baseline parameters.

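### Ten patients summarised descriptively, with no margin rule or upper limit, cannot establish a minimum safe PTV or PRV margin for later use

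*Combined protocol and SAP*

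**What the plan says.** The third exploratory objective in Section 11.4 is to "Determine the minimum safe planning target volume (PTV) and planning organ-at-risk volumes (PRV) to be subsequently utilized with the novel surface guidance system". The same objective stands in the Protocol Summary and in Section 2.2. On method, Section 11.4 says: "This will be determined through measurement evaluations in the first exploratory endpoint". That first endpoint compares surface guidance with breath-hold CBCT: "Geometric agreement will be evaluated by average symmetric surface distance (ASSD), modified Hausdorff distance (MHD), and Dice similarity coefficient measurements". The Protocol Summary words the endpoint as "Quantitative and qualitative measurement of minimum planning target volume (PTV) margins and planning organ-at-risk volumes to be subsequently utilized".

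Section 11.5 states that "we will also report descriptive statistics for treatment adaptation, dosimetry, geometric and phase agreement", and the list ends with "minimum acceptable PTV and PRV expansions for treatment planning". It closes: "As a pilot study we will establish these baseline parameters".

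The number of patients comes from Section 11.2: "A total of 10 evaluable patients (as defined in Section 5.2) will be included, with five treatment fractions each". That section justifies the size only for the rate of successful fraction delivery. It gives an anticipated in-patient correlation of 0.2 for that outcome.

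The documents give no formula from the agreement measures to a margin and no proportion of patients or fractions to be covered. They also give no confidence or tolerance limit, no split between patient-level and fraction-level error, and no precision statement for this objective.

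**The concern.** A margin described as the minimum that is safe, and meant for later use, is a claim about future patients. It depends on how much positional error varies between patients, and only ten patients inform that. More fractions, or more CBCT images (Section 5.1.8 recommends at most 10 per fraction, so at most 10 x 5 x 10 = 500), sharpen the within-patient part. They leave the between-patient part at 9 degrees of freedom.

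If a point estimate were reported under the present wording, a later user would have no way to see how far it could be from the truth. A PTV margin that is too small risks missing the target, and a PRV that is too small risks excess dose to an organ. Section 1.1 describes the harm from excess dose to adjacent structures and says that target margins compete with the space those structures occupy. An error in the other direction therefore also has a cost.

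**Working it through.** The plan states no precision or sample-size figure for this objective, so there is none to reproduce.

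**Inputs from the documents:** 10 patients and 5 fractions each (Section 11.2). **Assumptions not in the documents:** normally distributed errors unless stated; coverage targets of 90%, 95% and 99%; geometric within-patient correlation from 0 to 0.8. The 0.2 in Section 11.2 is for delivery success, not geometry.

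**1. Between-patient SD, 9 df.** The ratio s²/σ² follows chi-square(9)/9.
- Chance that s is below σ: P(chi-square(9) < 9) = 0.563.
- Lower 5% point of s/σ: √(3.325/9) = 0.608, so there is a 5% chance that the SD is understated by 39% or more.
- One-sided 95% upper factor: √(9/3.325) = 1.65.
- Two-sided 95% interval: 0.69 to 1.83 times the estimate.

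**2. Total SD, 10 patients x 5 fractions.** The total variance is estimated by MSB/5 + 4·MSW/5, with 9 df for MSB and 40 df for MSW. With total variance 1 and correlation ρ, the two expected parts are a = ρ + (1−ρ)/5 and b = 0.8(1−ρ). The Satterthwaite df is 1/(a²/9 + b²/40), and the upper factor is √(df / 5th percentile of chi-square).

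| ρ | a | b | df | chi-square 5th percentile | 95% upper factor |
|---|---|---|---|---|---|
| 0.2 | 0.36 | 0.64 | 40.6 | 26.99 | 1.23 |
| 0.5 | 0.60 | 0.40 | 22.7 | 12.88 | 1.33 |
| 0.8 | 0.84 | 0.16 | 12.7 | 5.66 | 1.50 |

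For comparison, 50 fractions taken as independent (49 df) give √(49/33.93) = 1.20.

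**3. Chance that the margin is undersized.** This depends on the rule, and the plan names none.
- Mean + z·s from 10 patient values (noncentral t): 0.538, 0.544 and 0.551 at 90%, 95% and 99% coverage.
- Empirical percentile of 50 pooled fractions, ρ from 0 to 0.8 (simulation): about 0.60 at 90% and 0.64 to 0.65 at 95%.
- Weighted sum of between- and within-patient SDs, ρ = 0.2 to 0.8 (simulation): 0.56 to 0.58 if the between-patient SD is corrected for within-patient noise. If it is not corrected, 0.17 to 0.23 at ρ = 0.2, 0.42 to 0.43 at ρ = 0.5, and 0.52 to 0.53 at ρ = 0.8.
- Largest of 10 patient values: 0.9^10 = 0.349, 0.95^10 = 0.599, 0.99^10 = 0.904.
- Largest of all 50 fractions, 90% and 95% coverage (simulation): 0.005 to 0.29.
- Skewed (lognormal, log-SD 0.5 to 0.8) errors, mean + z·s from 10 patient values (simulation): 0.59 to 0.73.

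**4. What an allowance for sampling error would look like.** A one-sided tolerance limit with 95% confidence from 10 patients uses 2.36 SD for 90% coverage (plug-in 1.28, ratio 1.84) and 2.91 SD for 95% coverage (plug-in 1.645, ratio 1.77). Without a distributional assumption, the observed maximum reaches 95% confidence only when 1 − P^n ≥ 0.95. That takes 29 patients for 90% coverage (1 − 0.9^29 = 0.953) and 59 for 95% coverage (1 − 0.95^59 = 0.952).

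**The case against.** The objective is exploratory, and Section 11.5 presents the results as a pilot's baseline parameters. Margins used in the trial itself are 3 to 7 mm at the physician's discretion (Section 5.1.3) and do not depend on this analysis, so no enrolled patient is exposed to the error. Descriptive statistics do not exclude an interval. No adoption procedure for the margins is given. All of this stands and limits the weight of the point. It supports calling the estimate preliminary, but it does not support calling it the safe minimum.

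The 1.65 factor belongs to the between-patient SD alone, and no section says that quantity will be used alone. For a total SD at correlation 0.2 the factor is 1.23, hardly different from the 1.20 for independent fractions. This also stands, and it is why the size is given as a range.

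Normal theory does not carry over directly to the named measures. ASSD and MHD are non-negative distances, and Dice is a unitless index between 0 and 1. That is fair, and it exposes the more basic gap: nothing says how these measures become a margin in millimetres.

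A reader might infer that images or fractions will be pooled as if independent. No section says so, and Section 11.2 recognises in-patient correlation for the primary endpoint. The plan is silent here, which is a different fault.

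**Conclusion.** The point holds as one of specification and wording. Ten patients, descriptive statistics, no conversion rule, no coverage target and no upper limit cannot support a conclusion that a margin is the safe minimum for later use.

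The size of the imprecision, assuming normal errors, is a one-sided 95% upper factor of 1.65 for a between-patient SD. For a total SD it is 1.23 to 1.50 over an assumed geometric correlation of 0.2 to 0.8.

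It is tempting to go further and say that the margin will more likely than not be too small. The documents do not support that. They name no rule and state no margin, and the chance moves from well below to well above one half with the rule, the coverage target and the shape of the errors. About 54-65% applies to common plug-in rules with normal errors. The 0.563 for a sample SD is not itself the chance of an undersized margin. Because the direction turns on an unstated choice, that choice should be made before the data are seen.

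**What to change.** In Sections 11.4 and 11.5, and in the matching text of the Protocol Summary and Section 2.2:

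- Replace *determine the minimum safe* with *estimate preliminary* margins, and say that they are subject to confirmation. Change *minimum acceptable* in Section 11.5 to match.
- State in advance how the geometric measurements convert to a PTV or PRV margin, and the coverage target the margin is meant to meet.
- Estimate between-patient and within-patient error separately, with the patient as the independent unit (for example, a mixed model with fractions and images nested in patients).
- Report a one-sided 95% upper confidence or tolerance limit beside the point estimate. The limit shows the uncertainty and does not by itself become the margin, since Section 1.1 notes that margins compete with adjacent organs.

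No margin value is proposed here. The change needs no further patients, images or procedures, only revised wording and a small variance-components analysis of data already collected. The downside is that the reported result will look less precise.

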Gated delivery of SBRT requires real-time monitoring of respiratory motion, most often using surrogates for the tumor motion. This can be accomplished using several technologies. One standard technique is real-time position management (RPM), with an infrared camera system mounted in the treatment room that monitors the movement of a reflective surrogate external marker block placed on the patient's abdomen or chest³⁰. A respiratory trace is generated based off of tracked surrogate motion and the beam can be gated on and off at desired phases or amplitude ranges of the respiratory cycle. However, use of a single external marker box alone to capture motion in a single plane may not robustly account for respiratory motion of an internal target and can result in errors in target localization of ~5mm in the SI plane³¹. RPM can be used in combination with periodic triggered intra-fraction imaging visualization of the tumor or internally placed fiducial markers to verify consistent correlation between the tumor and surrogate motion and improve accuracy, although an additional 2-3mm of uncertainty may remain^{31,32}. While more robust, fiducial placement and monitoring or even fiducial tracking-based deliveries are expensive, require an invasive procedure for fiducial implantation, lead to delays in initiation of treatment for marker placement and settling before simulation²⁸, and expose the patient to protracted treatment times³³ as well as additional imaging dose during delivery³⁴.

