An alternative and emerging technique is the use of optical surface image monitoring for continuous, non-invasive, and non-radiographic patient localization and respiratory tracking for SBRT. Surface guided radiotherapy can enable both breath-hold and amplitude phase-based gating, using a combination of light projectors to project a pattern of light onto the patient's surface and 2-3 optical cameras to generate and then track the motion of a 3-dimensional map of patient topography. Compared with techniques like RPM, monitoring of multiple surface points instead of a single surrogate marker improves accuracy of motion monitoring³⁵. Surface guidance motion monitoring has been shown to be accurate to 1mm motion/1degree of rotation in the delivery of intracranial stereotactic radiosurgery³⁶. It is also used to enable deep inspiratory breath hold (DIBH) gating in focal radiotherapy treatments like accelerate partial breast radiotherapy (APBI) to within 2mm of setup accuracy³⁷. Recently, it has been implemented for monitoring of internal target motion for lung and upper abdomen SBRT, and shown to accurately reflect internal anatomic shifts of 2mm or more compared to repeat cone beam CT alignment^{25 38}.

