2.2 Exploratory Objectives

1. Determine geometric agreement between breath-hold positioning as determined by a novel surface guidance system vs. concomitant breath-hold CBCT image sets.
2. Evaluate the compatibility of a standard-of-care respiratory gating system and the novel surface-guidance system for concomitant use.
3. Determine the minimum safe planning target volume and planning organ-at-risk volumes to be subsequently utilized with the novel surface guidance system.
4. Determine the local, in-field control rate at three months post-treatment.
5. Determine acute toxicity rates at three months post-treatment.
6. Identify patient and or treatment factors that maximize the potential efficacy of surface guided breath-hold respiratory gating, such as differences in surface topography and skin tone.

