5.1.8 Surface-Guided Gated Delivery

At time of CT and CBCT simulation, a baseline reference surface region of interest will be determined. The region of interest (ROI) will be selected on an individual basis for the most sensitivity to detect respiratory motion. At time of first treatment, the patient will be set up to marks and the reference surface. Breath-hold CBCT daily alignment image will be acquired and a new reference surface ROI will be established based on the daily anatomy. The reference surface will be monitored using the Identify system and a respiratory trace will be generated and displayed to the treatment team for breath-hold respiratory gating of treatment delivery. A visual feedback system will be displayed to the patient to aid in respiratory coaching for breath-hold. After treatment alignment and optional adaptation, a repeat breath-hold CBCT will be obtained to evaluate for any patient motion. Shifts can be applied as needed prior to initiation of delivery. CBCT can be repeated in the breath-hold position at set time points, e.g., after each arc in VMAT plans, and at the end of treatment delivery. A recommended maximum of 10 images will be taken per fraction. This will be used for intrafraction patient monitoring as well as subsequent evaluation of concordance between geometric patient position as identified by the Identify system vs. CBCT.

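### The minimum safe PTV and PRV margins are to come from an endpoint whose only named measures (ASSD, MHD, Dice) are unsigned, so they show neither direction nor persistent per-patient offset

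*Combined protocol and SAP*

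**What the plan says.** Section 2.2 sets the third exploratory objective: "Determine the minimum safe planning target volume and planning organ-at-risk volumes to be subsequently utilized with the novel surface guidance system". Section 11.4 gives the method: "This will be determined through measurement evaluations in the first exploratory endpoint". For that first endpoint it says: "Geometric agreement will be evaluated by average symmetric surface distance (ASSD), modified Hausdorff distance (MHD), and Dice similarity coefficient measurements". The matching endpoint in the Protocol Summary describes the margin measurement as both quantitative and qualitative, "as determined through measurement evaluations in exploratory endpoint 1", and names no other input.

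Section 11.5 lists minimum acceptable PTV and PRV expansions among the descriptive statistics, alongside dosimetry and geometric and phase agreement, and calls the results baseline parameters of a pilot.

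Section 5.1.8 describes the data. An alignment CBCT in breath-hold sets the daily reference surface. A repeat breath-hold CBCT follows, after which shifts may be applied. Further CBCTs are optional. The images serve monitoring and the later "evaluation of concordance between geometric patient position as identified by the Identify system vs. CBCT".

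The plan does not state the form of MHD, the structures compared, whether readings are taken before or after a shift, or the rule that turns a metric into a margin.

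**The concern.** A margin has to cover displacement. Displacement has a direction, and it splits into a part that recurs in the same patient and a part that varies from fraction to fraction. ASSD, MHD and Dice discard the sign before anything is summarised. Splitting the metric values by patient does not restore it, because the spread of an unsigned distance is not the spread of the displacement behind it.

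The protocol's own background uses directional or shift-based terms. Section 1.4.2 says that a single external marker "can result in errors in target localization of ~5mm in the SI plane", and describes surface guidance as "shown to accurately reflect internal anatomic shifts of 2mm or more compared to repeat cone beam CT alignment". Section 11.2 expects patient-level effects: "In-patient correlation is anticipated, as surface-guided delivery is in part patient-surface dependent".

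At stake is a figure labelled as safe and intended for later use. Two analysts could derive different margins from the same 10 patients, depending on the MHD form, structure, CBCT and rule they chose. From the named summaries alone, neither could show whether a patient was consistently offset, or in which direction.

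**Working it through.** The plan gives no margin, precision or power figure for this objective, so there is none to reproduce. The checks below ask what the named metrics can and cannot show.

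**Inputs from the documents:** 10 patients with 5 fractions each (section 11.2); PTV margin range of 3 to 7 mm (section 5.1.3); in-patient correlation of 0.2 (section 11.2, stated for delivery success and borrowed here). **Assumptions:** rigid shifts, spherical structures, and both a mean-based and a 95th-percentile form of MHD, because the form is not defined.

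**1. Same metrics, different displacement.** Take a 30 mm sphere and a 5 mm shift along one axis at all 50 fractions. At every fraction ASSD is 2.5 mm, mean-based MHD is 2.5 mm and Dice is 0.752. Three constructed cohorts share those values:

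| Cohort | Group mean (mm) | Between-patient SD (mm) | Within-patient SD (mm) | Size of patient mean (mm) |
|---|---|---|---|---|
| Sign fixed per patient, five +, five - | 0 | 5.27 | 0 | 5 |
| Sign alternates over fractions | 0 | 0 | 5.48 | 1 |
| Same offset in everyone | 5 | 0 | 0 | 5 |

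- Fixed sign: the patient means are five +5 and five -5, so the SD is sqrt(10 × 25 / 9) = 5.27.
- Alternating sign: within a patient, (5 × 25 - 5 × 1²) / 4 = 30, and sqrt(30) = 5.48. The between-patient variance estimate is 10/9 - 30/5, which is negative and set to 0.

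**2. Less extreme case.** For normal signed displacement with zero group mean and in-patient correlation r, the correlation of the absolute values is

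(2/π) × (sqrt(1 - r²) + r × asin(r) - 1) / (1 - 2/π).

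At r = 0.2 this is 0.035, and at r = 0.5 it is 0.22. The loss depends on the group mean. In simulation at r = 0.2, the unsigned correlation is 0.09, 0.15 and 0.20 for a group offset of 0.5, 1 and 2 SD. The loss is therefore large when offsets differ in sign between patients, and it disappears when everyone is offset the same way.

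**3. Why an undefined MHD and structure matter.** On a sphere the surface distance after a shift d is close to d × |cos θ|, and |cos θ| is uniform on 0 to 1. The mean is then 0.50 d (ASSD or mean-based MHD) and the 95th percentile is 0.95 d. The choice of form alone changes the reading by 0.95 / 0.50 = 1.9 times. Dice is 1 - 1.5(d/D) + 0.5(d/D)³ for a sphere of diameter D. At d = 5 mm it is 0.63, 0.75, 0.88 and 0.975 for D = 20, 30, 60 and 300 mm, the last being a body-sized structure.

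**4. What 10 × 5 fractions could support with signed data.** The one-sided 95% upper-limit factors are:
- SD of patient means (9 df): sqrt(9 / χ²(0.05, 9)) = 1.65.
- Within-patient SD (40 df): sqrt(40 / χ²(0.05, 40)) = 1.23.
- Between-patient component: sqrt((1 + k²/5) × 9 / χ²(0.05, 9) - k²/5), where k is the ratio of within to between SD and the within SD is treated as known. This is 1.75 at k = 1 and 2.02 at k = 2.

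A signed analysis is feasible but would be preliminary.

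**The case against.** Several points on the other side stand.

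- The three metrics are the only named inputs, but the plan does not say they are the exclusive ones. The Protocol Summary adds an undefined qualitative element, and section 11.5 reports dosimetry and phase agreement beside the margins without linking them to the margins.
- The loss lies in the summaries, not necessarily in the data. CBCT registrations keep direction, so signed shifts could be recovered if recording were planned. However, section 5.1.8 does not name shifts as a margin input, and no form in section 8.0 is dedicated to them.
- No section promises axis-specific margins, and section 5.1.3 gives one range without axes. A 95th-percentile distance could support a crude isotropic envelope.
- Section 11.5 already treats the expansions as descriptive, so part of the remedy is only to align the wording.
- The surface metrics capture deformation and rotation, which rigid displacement misses. That is a reason to keep them.

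A reader might infer that the trial will report margins about half the true displacement, because ASSD reads 0.50 of a shift on a sphere. The documents do not support this: nowhere do they say that a metric will be used directly as a margin. Nor do they support reading the 0.035 as the loss expected here. It needs a zero group mean and a correlation borrowed from a different outcome.

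**Conclusion.** The point holds in limited form. The stated route to the margins runs through unsigned summaries that cannot recover direction or separate persistent offset from scatter, and no conversion rule is given. That much follows from the text and from the definition of the metrics, and needs no numerical assumption. The numbers above are illustrations under rigid shifts and simple shapes; the documents give no basis for estimating the effect in this trial.

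The weight is moderate. The objective is exploratory, its result sets no margin in this study, and the primary feasibility test does not depend on it. It deserves correction because the output is described as safe and meant for later use, and because the section 5.1.8 images can support a better input. No margin value is proposed or implied.

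**What to change.** In section 11.4 and the matching Protocol Summary endpoint:

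- Keep ASSD, MHD and Dice as descriptive agreement measures. Define the form of MHD and the structures compared.
- Base the margin estimate on signed per-axis target and organ-at-risk displacement from the section 5.1.8 breath-hold CBCTs, leaving out the alignment CBCT that sets the daily reference.
- Record displacement at the repeat CBCT before any shift separately from residual displacement on later CBCTs where these were acquired.
- For each axis, report the mean, between-patient SD and within-patient SD, with upper confidence limits suited to the component and labelled preliminary (10 patients).
- State the conversion rule in advance.

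If displacement will not be recorded, replace the minimum safe label in the Protocol Summary objective and in sections 2.2 and 11.4 with wording that matches the descriptive language of section 11.5.

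The cost is SAP wording plus registration and recording work, including capture of any shift applied. Some residual readings will be missing because later CBCTs are optional, and the reported margins may look less favourable. The fallback costs wording only.
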